2.4 Coronary microvascular dysfunction: Diagnosis

Visualization of the coronary microcirculation is beyond the resolution of both invasive angiography and noninvasive coronary imaging modalities. Therefore, direct interrogation of coronary microvascular function is necessary to establish the diagnosis of CMD. Coronary flow reserve (CFR), calculated as the ratio of hyperemic to rest coronary blood flow, is a measure of coronary vasomotor function that integrates the hemodynamic effects of not only focal and/or diffuse epicardial disease but also small vessel disease on coronary blood flow in response to hyperemic pharmacologic (such as adenosine) or physiologic (exercise) stimuli. Therefore, in the absence of the obstructive epicardial disease, abnormal CFR is diagnostic of CMD. CFR can be measured by invasive coronary reactivity testing ¹¹ and non-invasive imaging modalities such as positron emission tomography (PET), cardiac magnetic resonance imaging and transthoracic echocardiography ¹². However, while these non-invasive imaging modalities are able to identify impaired CFR, they are not able to reliably evaluate the hemodynamic significance of a moderate or severe epicardial lesion and thus rule out the presence of concomitant obstructive CAD. On the hand, invasive angiography by combining the ability to exclude obstructive epicardial CAD, with complementary catheter-based

techniques to probe epicardial [by fractional flow reserve (FFR) or instantaneous flow reserve (iFR)] and microvascular coronary physiology [by CFR and hyperemic microvascular resistance (HMR)], is an accurate, comprehensive, and reproducible approach to evaluate patients with CMD. Accordingly (Figure 1):

- FFR (the ratio between coronary pressure distal to a stenosis and aortic pressure during maximal hyperemia, normal > 0.8) and iFR (the ratio between coronary pressure distal to a stenosis and aortic pressure during diastolic wave-free phase of the cardiac cycle, normal > 0.89) are used to rule out flow limiting lesions in epicardial arteries¹⁶⁻¹⁹. Both FFR and iFR are assessed using a pressure guidewire.
- CFR (the ratio of hyperemic over rest coronary blood flow) ≤ 2.5 is diagnostic of CMD in the absence of obstructive epicardial disease¹¹. It is most commonly assessed using an intracoronary Doppler-tipped guidewire or thermodilution techniques.

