3 HMR (the ratio of distal coronary pressure divided by coronary blood flow at maximal hyperemia using a combined pressure-flow intracoronary guidewire), similar to the index of microvascular resistance (IMR) [ratio of distal coronary pressure divided by the inverse of the mean transit time during maximal hyperemia using a pressure-thermodilution intracoronary guidewire and commercially available software], is a direct measure of microcirculatory resistance and is independent of epicardial vascular function. Using a combined pressure-flow wire, HMR ≥ 2.5 mHg/cm/s is diagnostic of CMD in the absence of obstructive epicardial disease and significant collateral coronary flow^{12, 20, 21}.

[figure not shown]

Figure 1: CFR: Coronary flow reserve; FFR: Fractional flow reserve; IMR: Index of microvascular resistance

2.5 Coronary microvascular dysfunction: Current limited treatment options and unmet clinical need

Small, short-term studies of symptomatic patients with ischemia but no obstructive CAD using anti-atherosclerotic and/or anti-ischemic agents have produced limited symptomatic, ischemic, or functional improvement. Accordingly, in the absence of large randomized controlled trials demonstrating effective therapies for CMD, existing guidelines focus on reassurance and symptom management^{22, 23} with current standard therapy mostly extrapolated from obstructive epicardial coronary artery disease and consisting of cardiovascular risk factors control, statins and traditional antianginal therapies, such as beta-blockers, calcium channel blockers, and long-acting nitroglycerine^{24, 25}. Angiotensin converting enzyme inhibitors, L-arginine and aspirin may also sometimes be used for treatment of CMD²⁴⁻²⁶. CORMICA, a randomized controlled blinded clinical trial of stratified medical therapy versus standard care in patients with angina and non-obstructive angiographic CAD, showed that invasive assessment of the microvascular function at the time of the coronary angiogram as a

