- Patients with chronic refractory angina (CCS class II-IV), no obstructive CAD (<50% stenosis in epicardial vessels and/or iFR>0.89 or FFR>0.8 in vessels with 50 to 70% stenosis), and documented CMD (CFR≤2.5 and/or HMR≥2.5) & or coronary blood flow (CBF) response to acetylcholine ≤ 50%.on clinically indicated coronary angiography and invasive coronary reactivity testing which uses Adenosine, Acetylcholine & Nitroglycerin as standard clinical practice will be eligible for enrolment.
- A full clinically indicated coronary flow evaluation will be performed in the left anterior descending artery (LAD) as standard of care using an intracoronary combined Doppler-flow and pressure wire (ComboWire XT, Philips Volcano Corporation, Del Mar, California) that provides iFR/FFR, HMR and CFR measurements. This will determine patient eligibility. If patients are deemed eligible, and wish to participate, they will go through the informed consent process to enroll in the study after their procedure.
- Baseline clinical evaluations of eligible patients will include clinical characteristics, medication profiles including antianginals, evaluation of angina severity and frequency by CCS angina class and Seattle Angina Questionnaire (SAQ), in addition to ischemia, exercise capacity, and left ventricular diastolic function and filling pressures at peak exercise on an exercise bike echocardiographic stress test (EBEST)

using a supine bike protocol starting at 25 Watts and increasing by 25 Watts every 2 minutes.

- Eligible patients will undergo percutaneous implantation of The Neovasc Reducer™ System (Neovasc Inc., Richmond, B.C., Canada) for the treatment of CMD.
- Adverse events will be collected during the 4 months study period and monthly follow-up phone calls with study participants will be conducted at 1, 2, and 3 months post CS reducer implant
- Study participants will undergo full repeat invasive evaluation of coronary blood flow and microvascular resistance (CFR and HMR) as well as repeat clinical evaluation (including CCS class, SAQ, antianginal medication use, adverse events, and EBEST) at 4 months following Reducer implantation.

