8.3 Subject Compliance Monitoring:

There will be no assessment of compliance as the device will be implanted in the cath lab, and there are no further drugs that need to be administered.

9- Coronary Reactivity Testing

A full clinically indicated coronary flow evaluation will be performed in the left anterior descending artery (LAD) as standard of care to determine study eligibility using an intracoronary combined Doppler-flow and pressure wire (ComboWire XT, Philips Volcano Corporation, Del Mar, California) that provides iFR/FFR, HMR and CFR measurements. In cases in which assessment cannot be performed in the LAD, coronary reactivity testing may be done in the left circumflex (LCx) artery. In brief, after engaging the coronary artery of interest with a guiding catheter, FFR or iFR will first be done in case of moderate (>50 to <70%) epicardial disease to document non-obstructive CAD (FFR>0.8 or iFR>0.89) as was previously described in section 2.4. In cases of mild (<40%) epicardial disease by angiography, FFR/iFR is not recommended but may be done at the discretion of the operator. After confirming non-obstructive epicardial CAD (no CAD, mild CAD<40% or negative FFR/iFR for moderate CAD >50 but <70%), the ComboWire XT will be inserted and parked in the mid LAD for measurement of CFR and HMR. Intracoronary bolus injections of incremental doses (36, 60 and 72 µg) of adenosine will be administered until maximal hyperemia is achieved or the largest dose was given ¹¹. CFR will be measured as the average hyperemic blood velocity post adenosine/average baseline velocity. Highest achieved CFR

will be used for analysis. A cine image of the LAD will be obtained after each adenosine administration. Coronary artery diameter will then be measured offline by an independent investigator in the segment 5 mm distal to the tip of the pressure-flow wire with a quantitative coronary angiography program (Medis Corp, Leiden, the Netherlands) as described previously^{46, 47} and coronary blood flow (CBF) will then be calculated from the Doppler-derived time velocity integral and vessel diameter, where $CBF = \pi \times (\text{coronary artery diameter}/2)^2 \times (\text{average peak hyperemic velocity}/2)$ ⁴⁸. HMR will then be calculated as distal coronary pressure divided by coronary blood flow at maximal hyperemia. For binary analysis, CMD will be defined as $CFR \leq 2.5$ and/or $HMR \geq 2.5$ ^{11, 12, 20, 21}.

10- Prior and Concomitant Therapy

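### Section 9 divides distal pressure by a volumetric flow to obtain HMR, then applies a 2.5 cut-off that Section 2.4 states per unit of velocity

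*Combined protocol and SAP*

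**What the plan says.** **Section 9 (Coronary Reactivity Testing)** takes three steps in sequence.

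- Flow: "coronary blood flow (CBF) will then be calculated from the Doppler-derived time velocity integral and vessel diameter", with CBF = π × (diameter/2)² × (average peak hyperemic velocity/2). The diameter is measured offline by quantitative coronary angiography (QCA).
- Resistance: "HMR will then be calculated as distal coronary pressure divided by coronary blood flow at maximal hyperemia".
- Classification: for binary analysis, microvascular dysfunction is CFR ≤ 2.5 and/or HMR ≥ 2.5. No unit is given for HMR or CBF.

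**Section 2.4** words HMR in the same way, as "the ratio of distal coronary pressure divided by coronary blood flow at maximal hyperemia using a combined pressure-flow intracoronary guidewire", but attaches a unit to the cut-off: an HMR of at least 2.5 "mHg/cm/s is diagnostic of CMD in the absence of obstructive epicardial disease". The mHg is evidently a slip for mmHg. The unit is pressure per velocity.

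**Use of HMR.** Section 7.1 lists HMR ≥ 2.5, without a unit, among the inclusion indices. Section 6.2 makes change in CFR and HMR at 4 months the primary endpoint, and Section 12 analyses absolute and percent change.

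**Source of the value.** Sections 6.1 and 9 say that the combined pressure and Doppler wire supplies HMR, and Section 6.1 says of that evaluation: "This will determine patient eligibility". Section 9 nevertheless sets out an offline calculation for the same test. The Section 11.8 schedule marks CFR and HMR only at Day 120, so the eligibility test is also the baseline.

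**The concern.** Area times velocity is a volume per unit time. Pressure divided by it is not the quantity to which a cut-off in mmHg/(cm/s) belongs, and the conversion between the two depends on vessel diameter, which varies between patients.

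Two things are at stake. First, if Section 9 is followed literally for eligibility, a patient who would qualify on HMR alone is classified partly by vessel size and by an unstated flow unit. Second, half of the primary endpoint has two possible values, one from the wire and one calculated offline. Sections 11.7 and 12 do not say which is analysed, so the choice could be made after both are known.

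**Working it through.** **Inputs from the documents:** the CBF and HMR formulas and the cut-off of 2.5 (Section 9); the cut-off unit, pressure per cm/s (Section 2.4).

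**Assumptions, because the documents give no figure:** diameters D of 2, 2.5, 3 and 4 mm; CBF in mL/min, with mL/s also shown; QCA reading errors of 3%, 5% and 7%.

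**Conversion.** Write Pd for distal pressure and v for average peak hyperemic velocity.

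Pd/CBF = Pd / [π(D/2)² × v/2] = (Pd/v) × 8/(πD²)

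With D in cm this is in mmHg/(mL/s); divide by 60 for mmHg/(mL/min). At D = 0.3 cm: 8/(π × 0.09) = 28.29, and 28.29/60 = 0.472.

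| | 2 mm | 2.5 mm | 3 mm | 4 mm |
|---|---|---|---|---|
| Factor, mL/min | 1.061 | 0.679 | 0.472 | 0.265 |
| Section 9 value when Pd/v = 2.5 (mL/min) | 2.65 | 1.70 | 1.18 | 0.66 |
| Section 9 value when Pd/v = 2.5 (mL/s) | 159 | 102 | 71 | 40 |
| Pd/v when the Section 9 value is 2.5 (mL/min) | 2.36 | 3.68 | 5.30 | 9.42 |
| Section 9 value when Pd/v = 3.0 (mL/min) | 3.18 | 2.04 | 1.41 | 0.80 |
| Absolute fall of 0.5 in Pd/v (mL/min) | 0.53 | 0.34 | 0.24 | 0.13 |

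**Direct check.** Take illustrative values Pd = 85 mmHg and v = 34 cm/s, so Pd/v = 2.5. At 3 mm, CBF = π × 0.15² × 17 × 60 = 72.1 mL/min, and 85/72.1 = 1.18, as in the table.

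**Where the scales agree.** In mL/min the factor equals 1 only at D = 10 × √(8/(60π)) = 2.06 mm.

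**Effect on classification.** In mL/min, a patient at Pd/v = 3.0 is abnormal by Section 2.4 but falls below 2.5 at 2.5, 3 and 4 mm. A patient at Pd/v = 2.4 is not abnormal by Section 2.4 but scores 2.4 × 1.061 = 2.55 at 2 mm and would pass. In mL/s, a Section 9 value of 2.5 corresponds to a Pd/v of only 0.04 to 0.16, so essentially every patient would pass.

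**Effect on the change score.** If diameter is the same at both visits, percent change is identical on the two scales; absolute change is not (last row of the table). A QCA reading error at one visit enters Pd/CBF squared:

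- 3%: 1.03⁻² − 1 = −5.7%; 0.97⁻² − 1 = +6.3%
- 5%: 1.05⁻² − 1 = −9.3%; 0.95⁻² − 1 = +10.8%
- 7%: 1.07⁻² − 1 = −12.7%; 0.93⁻² − 1 = +15.6%

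Conversely, a true calibre change of +5% or −5% at fixed pressure and flow moves Pd/v by 1.05² − 1 = +10.3% or 0.95² − 1 = −9.8%, and leaves Pd/CBF unchanged.

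**The case against.** The unit conflict itself is not in dispute. The arguments against giving it weight are these.

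- **Loose wording.** Both sections describe HMR in the same words, and Section 2.4 uses blood flow loosely elsewhere: CFR is "calculated as the ratio of hyperemic to rest coronary blood flow", yet Section 9 says "CFR will be measured as the average hyperemic blood velocity post adenosine/average baseline velocity". This explains Section 2.4. It does not rescue Section 9, which keeps velocity and flow apart and puts an explicit area formula directly before the HMR sentence.
- **Eligibility probably uses the wire value.** The text does lean that way, and the 2.5 in Section 9 is introduced for a binary analysis that Section 12 does not plan. But Section 9 opens by presenting this test as the one that determines eligibility and then prescribes the offline calculation. The source is therefore ambiguous, and misclassification is a risk rather than an established fact.
- **The sizes are conditional.** This stands. They rest on assumed diameters and an assumed flow unit, and in mL/min a wrongful pass needs a vessel under 2.06 mm. The mismatch itself needs no assumed diameter.
- **The endpoint is a change.** Pd/CBF used at both visits is still a resistance measure, percent change is unaffected if diameter is stable, and Section 6.1 calls for the full evaluation to be repeated, which suggests one method. All of this stands, but Section 12 also analyses absolute change, and no section names the endpoint value.
- **Neither formula is free of error.** This also stands: QCA error harms one and true calibre change the other, by similar amounts. For the cut-off, however, the protocol's own unit settles the matter.

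**Conclusion.** The concern holds. Section 9, the only operational definition of HMR, yields a different quantity from the one to which the 2.5 cut-off belongs, and no other section supplies a CBF unit, a conversion or a volumetric cut-off. This is an error in the text as written, and it should be corrected before HMR is used for eligibility or analysis.

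Under the assumed diameters, the velocity-based threshold that a Section 9 value of 2.5 implies runs from 2.36 to 9.42 mmHg/(cm/s) if CBF is in mL/min, and is close to zero if CBF is in mL/s. Only patients who qualify on HMR alone are exposed at entry. The CFR and acetylcholine routes are not affected, and the documents do not allow the number exposed to be estimated. For the primary endpoint the damage is narrower: added QCA error, an absolute change that is not in the unit of the cut-off, and an undeclared choice between two HMR values.

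**What to change.** Reconcile Sections 2.4 and 9 to one HMR formula, unit and source, apply it identically at the eligibility/baseline test and at Day 120, and name it in Sections 9, 11.7 and 12.

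- To match the protocol's own cut-off unit, define HMR as mean distal coronary pressure divided by average peak velocity at maximal hyperemia, in mmHg/(cm/s), from the combined-wire recording.
- Correct the references to coronary blood flow in the HMR definitions of both sections, and the mHg slip in Section 2.4.
- Keep the diameter-based formula for CBF only, and state its unit.
- Optionally report change in Pd/CBF, without the 2.5 cut-off, as a sensitivity analysis. This would show whether a calibre change between visits matters, which is the one weakness of the velocity form.

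The cost is protocol wording: the wire already records pressure and velocity, and QCA is already planned for CBF. If any HMR has already been derived by the offline formula, it would need to be recalculated from the recorded pressure and velocity.

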11.1 Visit 1: Screening Visit

The screening visit will take place within 30 days before CS Reducer implantation, primary safety endpoints and secondary endpoints. Information on safety will be captured between visits on a diary card.

Screening Visit:

- Informed consent

- Demographic data
- Medical and surgical history
- Medication history
- Concomitant medication
- Concomitant procedures
- Vital signs, including height and weight
- 12 Lead ECG
- Physical exam
- Pregnancy test (blood) in reproductive-age woman

Based on results of screening test and review of eligibility criteria, PI will assess subject's eligibility for study inclusion. If deemed eligible, the patient will be enrolled in an open study cohort. Screening visit results will be recorded in the subjects electronic case report form and the subject will be scheduled for CS Reducer implantation procedure.

11.2 Pre-Implant Days -21 to -1

- Vital signs
- 12-lead ECG
- Recording of concomitant medications
- Recording of adverse events
- Evaluation of angina severity and frequency by CCS angina class
- Evaluation of quality of life by SAQ
- Standard pre-procedural laboratory tests including hematology and blood chemistry.
- Evaluation of ischemia, exercise capacity, and left ventricular diastolic function and filling pressures at peak exercise on EBEST

11.3 Implant day 0

- Vital signs
- 12-lead ECG
- Limited physical examination
- CS Reducer implantation
- Recording of adverse events
- Recording of concomitant medications

11.4 Post-Implant day 30 (± 4 Days)

- Phone call to assess:
 - CCS angina class assessment
 - SAQ assessment
 - Adverse events
 - Concomitant medications

11.5 Post-Implant day 60 (± 7 Days)

- Phone call to assess:
 - CCS angina class assessment
 - SAQ assessment
 - Adverse events
 - Concomitant medications

11.6 Post-Implant day 90 (± 7 Days)

- Phone call to assess:
 - CCS angina class assessment

- SAQ assessment
- Adverse events
- Concomitant medications

11.7 Post-Implant day 120 (± 14 days)

- Vital signs
- 12-lead ECG
- CCS angina class assessment
- SAQ assessment
- Adverse events
- Concomitant medications
- Limited physical exam
- Standard laboratory tests including hematology, blood chemistry, liver function tests, CRP and creatinine, urinalysis
- Evaluation of ischemia, exercise capacity, and left ventricular diastolic function and filling pressures at peak exercise on EBEST
- Coronary angiography and reactivity testing to measure CFR and HMR

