10 PRIOR AND CONCOMITANT THERAPY.....	30
11 STUDY PROCEDURES.....	30
11.1 VISIT 1: SCREENING VISIT	30
11.2 PRE-IMPLANT DAY 1-5	31
11.3 IMPLANT DAY 0	32
11.4 POST-IMPLANT DAY 30	32
11.5 POST-IMPLANT DAY 60	33
11.6 POST-IMPLANT DAY 90	33
11.7 POST-IMPLANT DAY 120	33
11.8 SCHEDULE OF STUDY PROCEDURES AND ASSESSMENTS.....	34
12 STATISTICAL PLAN	35
13 SAFETY AND ADVERSE EVENTS.....	36
13.1 DEFINITIONS.....	36

13.2 ADVERSE EVENTS.....	38
13.3 SERIOUS ADVERSE EVENTS	38
13.4 ADVERSE EVENT REPORTING PERIOD.....	39
13.5 PREEEXISTING CONDITION.....	40
13.6 GENERAL PHYSICAL EXAMINATION FINDINGS	40
13.7 POST-STUDY ADVERSE EVENTS.....	40
13.8 PATIENTS ON ANTICOAGULANTS AND ANTIPLATELETS.....	40
13.9 HOSPITALIZATION, PROLONGED HOSPITALIZATION OR SURGERY	41
13.10 RECORDING OF ADVERSE EVENTS	42
13.11 REPORTING OF SERIOUS ADVERSE EVENTS AND UNANTICIPATED PROBLEMS	42
13.12 SPONSOR-INVESTIGATOR REPORTING: NOTIFYING THE MAYO IRB	43
13.13 SPONSOR-INVESTIGATOR REPORTING: NOTIFYING THE FDA.....	44
13.14 STOPPING RULES.....	45
13.15 MEDICAL MONITORING	45
14 DATA HANDLING AND RECORD KEEPING.....	45
14.1 CONFIDENTIALITY	46
14.2 SOURCE DOCUMENTS.....	47
14.3 CASE REPORT FORMS.....	47
15 DATA MANAGEMENT	48
15.1 DATA QUALITY ASSURANCE	48
15.2 DATA CLARIFICATION PROCESS	48
15.3 RECORDS RETENTION.....	48
16 STUDY MONITORING, AUDITING, AND INSPECTING	49
16.1 STUDY MONITORING PLAN.....	49
16.2 AUDITING AND INSPECTING	50
17 ETHICAL CONSIDERATIONS	50
18 STUDY FINANCES.....	51
13.1 FUNDING SOURCE.....	51
13.2 CONFLICT OF INTEREST	51
19 PUBLICATION PLAN.....	51
20 REFERENCES.....	53

Study synopsis

Title	A Phase II Study Testing the Feasibility and Efficacy of Coronary Sinus Narrowing in Patients with Coronary Microvascular Dysfunction
Study objective	To evaluate the impact of the Neovasc Reducer™ device implantation on coronary microvascular function assessed invasively by measurement of coronary flow reserve (CFR) and the hyperemic myocardial resistance (HMR) in patients with angina but no-obstructive coronary artery disease (ANOCA) and documented coronary microvascular dysfunction (CMD) [CFR \leq 2.5 and/or HMR \geq 2.5] or coronary blood flow (CBF) response to acetylcholine \leq 50%.
Study hypothesis	In patients with ANOCA and documented CMD, narrowing of the CS by Reducer implantation will improve microvascular function as measured by CFR and HMR, and quality of life
Device	The Neovasc Reducer™ System (Neovasc Inc., Richmond, B.C., Canada)

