Study design	
 • Prospective, single center, single arm, clinical trial • Patients with chronic refractory angina (Canadian Cardiovascular Society (CCS) grade II-IV, no obstructive CAD (<50% stenosis in epicardial vessels and/or iFR$>$0.89 or FFR$>$0.8 in vessels with 50 to 70% stenosis), and documented CMD (CFR\leq2.5 and/or HMR\geq2.5) or coronary blood flow (CBF) response to acetylcholine \leq 50% on clinically indicated coronary angiography and invasive coronary reactivity testing which uses Adenosine, Acetylcholine & Nitroglycerin as standard clinical practice will be eligible for enrolment.

	
 • After a full clinically indicated coronary flow evaluation is performed in the left anterior descending artery (LAD) as standard of care using an intracoronary combined Doppler-flow and pressure wire (ComboWire XT, Philips Volcano Corporation, Del Mar, California) that provides iFR/FFR, HMR and CFR measurements, patients will be determined eligible. • Baseline clinical evaluations of eligible patients will include clinical characteristics, medication profiles including antianginals, evaluation of angina severity and frequency by CCS angina class and Seattle Angina Questionnaire (SAQ), in addition to ischemia, exercise capacity, and left ventricular diastolic function and filling pressures at peak exercise on an exercise bike echocardiographic stress test (EBEST) using a supine bike protocol starting at 25 Watts and increasing by 25 Watts every 2 minutes. • Eligible patients will undergo percutaneous CS Reducer implantation for the treatment of CMD. • Adverse events will be collected during the 4 months study period and monthly follow-up phone calls with study participants will be conducted at 1, 2, and 3 months post CS reducer implant • Study participants will undergo full repeat invasive evaluation of coronary blood flow and microvascular resistance (CFR and HMR) as well as repeat clinical evaluation (including CCS class, SAQ, antianginal medication use, adverse events, and EBEST) at 4 months following Reducer implantation.
Number of subjects	30

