6.2 Primary Endpoint

Change in CFR and HMR measurements at 4 months post CS Reducer implantation compared to baseline

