6.3 Secondary Endpoints

- Change in CCS angina class
- Change in the score of all 5 domains of the Seattle Angina Questionnaire for assessing quality of life
- Change in the consumption and frequency of short acting nitrates (spray or sublingual tablets)
- Change in EBEST parameters at 4 months compared with baseline (total exercise duration, time to 1 mm ST segment depression, evidence of ischemia, peak exercise stage, peak exercise diastolic function and filling pressures as measured by echocardiographic E/e', and exercise-induced symptoms)

- Procedural-related Major Adverse Cardiac Events (MACE) defined as: death, myocardial infarction, perforation of the CS, CS total occlusion, or need for urgent dilatation of the Reducer within 4 months of follow-up

7- Study Population:

Patients with chronic refractory angina (CCS class II-IV), no obstructive CAD (<50% stenosis in epicardial vessels and/or iFR>0.89 or FFR>0.8 in vessels with 50 to 70% stenosis), and documented CMD (CFR≤2.5 and/or HMR≥2.5) & or coronary blood flow (CBF) response to acetylcholine ≤ 50%. on clinically indicated coronary angiography and invasive coronary reactivity testing which uses Adenosine, Acetylcholine & Nitroglycerin as standard clinical practice

7.1 Inclusion Criteria:

- Age ≥ 18
- Able to provide written informed consent and willing to participate in all required study follow-up assessments
- Symptomatic CAD with refractory angina defined as CCS class II to IV, despite optimal tolerated medical therapy for more than 3 months.
- Abnormal coronary microvascular function indices: CFR≤2.5 and/or HMR≥2.5 & or coronary blood flow (CBF) response to acetylcholine ≤ 50%.

7.2 Exclusion Criteria:

- Recent (within 3 months) acute coronary syndrome
- Recent (within 6 months) percutaneous coronary intervention revascularization by stent
- Patients with prior coronary artery bypass surgery

- Unstable angina (recent onset angina, crescendo angina, or rest angina with ECG changes) during the last 30 days
- Subjects in cardiogenic shock (systolic pressure < 80mm/Hg, on vasopressors or intraaortic counter pulsation) at the time of consenting. Subjects who recover from cardiogenic shock by the time of consenting are eligible.
- Obstructive CAD on coronary angiography (>70% stenosis or 50-70% stenosis with $iFR \leq 0.89$ or $FFR \leq 0.8$ in epicardial artery)
- Inability to perform invasive coronary flow evaluation and/or measure CFR and HMR in the LAD
- Severe valvular heart disease

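### Patients may qualify on an acetylcholine flow response alone, but microvascular outcome is only CFR and HMR, where those patients start on the normal side of both thresholds

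*Combined protocol and SAP*

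**What the plan says.** **Entry.** In the synopsis, the objective and study design rows join the acetylcholine criterion to the CFR/HMR criterion with a plain or: "or coronary blood flow (CBF) response to acetylcholine", with a cut-off of 50%. The synopsis population and inclusion rows, and Sections 6.1, 7 and 7.1, put an ampersand before that or, so it is unclear whether the criterion is an alternative or an addition. The Project Summary and the binary definition of CMD at the end of Section 9 use CFR and HMR only and leave acetylcholine out.

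**Qualifying test.** Section 6.1 describes "invasive coronary reactivity testing which uses Adenosine, Acetylcholine & Nitroglycerin as standard clinical practice". Section 9, which gives the measurement method, describes adenosine only.

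**Outcomes.** The primary endpoint (Section 6.2) is "Change in CFR and HMR measurements at 4 months post CS Reducer implantation compared to baseline". The secondary endpoints (Section 6.3) are CCS class, SAQ domains, short-acting nitrate use, exercise echocardiography parameters and procedural MACE. Section 12 evaluates microvascular function through CFR and HMR alone.

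**Day 120.** Section 11.7 lists "Coronary angiography and reactivity testing to measure CFR and HMR", and the schedule in Section 11.8 agrees. Section 6.1 calls this a "full repeat invasive evaluation of coronary blood flow and microvascular resistance (CFR and HMR").

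**The concern.** Eligibility is wider than the outcome. A patient admitted only because the flow response to acetylcholine was low has, by construction, no abnormal CFR or HMR to correct. Two things follow.

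- **Dilution.** The primary analysis averages these patients with those whose CFR or HMR was abnormal, so an effect in the second group can be diluted.
- **No outcome on the qualifying abnormality.** Nothing planned shows whether the acetylcholine response moved. Section 2.3 attributes adenosine-type responses largely to relaxation of vascular smooth muscle, so the plan gives no basis for letting CFR or HMR stand in for it.

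Aim 5.5 says the trial should supply the information needed to design pivotal studies. Whether to carry the acetylcholine route into those studies is one such decision, and this plan would not inform it.

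**Working it through.** **1. Who is affected under each reading of eligibility**

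| Reading | Supported by | Consequence |
|---|---|---|
| Acetylcholine is an alternative route | Synopsis objective and study design (plain or) | Acetylcholine-only patients exist; dilution and the missing outcome both apply |
| Acetylcholine is required in addition | One reading of the ampersand in the synopsis population and inclusion rows and Sections 6.1, 7, 7.1 | No acetylcholine-only group, so no dilution; but every patient has an acetylcholine abnormality that is not followed |
| Acetylcholine is not part of CMD | Project Summary; binary definition in Section 9 | Neither issue arises |

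Only the first reading fits the plain or. The steps below use it.

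**2. Baseline status.** Failing the criterion CFR≤2.5 and/or HMR≥2.5 means CFR>2.5 and HMR<2.5. An acetylcholine-only patient is therefore on the normal side of both primary measures.

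**3. Search for an acetylcholine outcome.** Sections 6.2, 6.3, 11.7, 11.8 and 12 contain none. Section 9 has no acetylcholine procedure and no definition of percent flow response. Its cine images follow each adenosine dose, and its flow formula uses hyperemic velocity.

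**4. Illustration of dilution.** The plan states N = 30 without alpha, power, effect size or SD, so there is no power figure to reproduce. Let f be the acetylcholine-only share (not stated; assumed 10% to 50%). Assume those patients have zero expected change in CFR/HMR and that the SD of change is the same as without them. Then:

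- number of acetylcholine-only patients = 30f
- mean change = (1−f) × the change in CFR/HMR-abnormal patients
- N for a given power is proportional to SD²/(mean change)² (normal approximation), so it is multiplied by 1/(1−f)²

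| f | Patients of 30 | Mean change retained | Multiplier on N |
|---|---|---|---|
| 10% | 3 | 0.90 | 1/0.81 = 1.23 |
| 20% | 6 | 0.80 | 1/0.64 = 1.56 |
| 30% | 9 | 0.70 | 1/0.49 = 2.04 |
| 50% | 15 | 0.50 | 1/0.25 = 4.00 |

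On the same assumptions, at f = 30% the mixed group of 30 carries the information of 30 × 0.49 = 14.7 CFR/HMR-abnormal patients. Analysing the 30 × 0.70 = 21 such patients separately uses all 21. Reporting by route therefore deals with the dilution.

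**5. Precision in the acetylcholine-only group.** The 95% half-width for a mean change is t/√n in SD units. For n = 3 it is 4.303/√3 = 2.48 SD; for n = 15 it is 2.145/√15 = 0.55 SD. Any result in this group will be descriptive.

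**The case against.** The strongest defence is that endpoint and objective agree. The objective, both statements of the hypothesis, Aim 5.1, Section 6.2 and Section 12 all name CFR and HMR. In the objective, acetylcholine appears only in describing who is enrolled, and a trial need not turn every eligibility variable into an outcome. This stands. It rules out calling the primary endpoint wrong, but it does not remove the dilution or the need to say how far the conclusion reaches.

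Some stronger inferences should be resisted:

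- A reader might infer that a null result would be reported for patients in whom nothing was tested. The documents do not support this. Inability to measure CFR and HMR is an exclusion, repeat testing is planned for everyone, and symptoms, nitrate use and exercise outcomes are also followed in everyone.
- A reader might infer that acetylcholine is beyond doubt a stand-alone route. The ampersand wording, and the two places that omit acetylcholine, leave this open.
- A reader might infer that a Day 120 acetylcholine value is already being collected and ignored. The phrase about a full repeat allows that possibility, but its brackets name only CFR and HMR.
- A reader might infer that the Day 120 test must include acetylcholine. That could add a procedure to a research catheterization, and the point does not depend on it.

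**Conclusion.** The point holds in limited form. If the plain or governs, acetylcholine-only patients can dilute the primary mean change, and the trial will be silent on whether their qualifying abnormality changed. The results on CFR, HMR and clinical outcomes are not invalidated.

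The size is unknown because the share of such patients is not stated. The 10% to 50% range is an assumption, and the dilution figures also assume no CFR/HMR change in these patients and an unchanged SD. If the eligibility text is settled so that acetylcholine is not an alternative route, the dilution disappears. The change is worth making because most of it is wording and one extra breakdown of data already planned.

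**What to change.** 1. Reconcile the definition of CMD across the synopsis, Project Summary and Sections 6.1, 7, 7.1 and 9, so that it is clear whether acetylcholine is an alternative, an addition, or not a criterion.
2. In Section 12, report change in CFR and HMR overall and separately for patients with abnormal CFR and/or HMR and for acetylcholine-only patients. Treat the comparison as descriptive: the two groups are selected on opposite sides of the baseline thresholds, so regression to the mean would push them in opposite directions.
3. State in Sections 9 and 11.7 whether the Day 120 test includes acetylcholine. If it does, pre-specify in Sections 6.3 and 12 the change in percent flow response to acetylcholine as a secondary endpoint. Report it for all patients with paired values and for those who entered at 50% or below. Add its measurement definition to Section 9, and note that selection on a low baseline in a single arm invites regression to the mean.
4. If it does not, state that the efficacy conclusion is limited to CFR and HMR and does not extend to the acetylcholine abnormality.

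The cost is protocol and SAP wording, a short method description if item 3 applies, and a small, imprecise subgroup analysis. No new provocation test is required.
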